#### 10.7.2.5. Patient Reported Outcome (PRO) by EQ-5D-5L

For EQ-5D-5L, the scores for the five categorical dimensions will be used to compute a single utility score ranging from zero (0.0) to one (1.0) representing the general health status of the subject. The United Kingdom weights will be used to generate subject utilities from the five dimensions.

The change in utility score from baseline will be summarized. Methods will be detailed in SAP.

### **10.7.3. Exploratory Endpoints and Methods**

The exploratory endpoints will be evaluated to comparing the treatment effects between two treatment arms. Descriptive statistics will be used to summarize these exploratory endpoints. The details will be provided in the SAP.

#### **10.7.3.1. Event-free Survival**

Event-free survival is measured by the absence of events defined by progressive disease (PD), death, and nonresponders.

#### **10.7.3.2. Time to Next Treatment (TTNT)**

Time to next treatment (TTNT) is defined as the time from randomization to institution of any subsequent treatment for CLL/SLL (including the next line ibrutinib for subjects in arm B).

#### **10.7.3.3. Clonal Evolution**

The proportion of subjects with new cytogenetic abnormalities (del 11q, del 17p, or trisomy 21), or other cytogenetic abnormalities detected by FISH, cytogenetics, or mutational analysis at any time post commencement of study treatment will be determined.

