#### ***For Evaluation of Clonal Evolution***

A bone marrow sample should also be collected at the time of disease progression for examination of clonal evolution (acquisition of new cytogenetic abnormalities defined as new del 11q, del 17p, or trisomy 12 by FISH, or other cytogenetic abnormalities).

***For Assessment of Minimal Residual Disease (MRD)*** A peripheral blood and bone marrow aspirate will be collected from all subjects at Cycle 9 and in those with a suspected CR after the start of study treatment, for assessment of MRD status.

- All responders who have an MRD-negative status in the bone marrow, should be followed with peripheral blood MRD assessments every 4 cycles until Cycle 33 then every 6 cycles starting at Cycle 39.
- All responders who have an MRD-positive status in the bone marrow or peripheral blood, should also be followed with peripheral blood MRD assessments every 4 cycles until Cycle 33 then every 6 cycles starting at Cycle 39. Once the subject becomes MRD-negative in the peripheral blood, this result should be subsequently confirmed with a bone marrow MRD assessment.
- A bone marrow aspirate will not be required at Cycle 9 for subjects who have unequivocal evidence of ongoing gross clinically detectable disease (eg, lymph node >2 cm), however these subjects should have a peripheral blood sample sent for MRD analysis and a bone marrow aspirate should be considered for the next scheduled response assessment visit.

The following material will be sent to the central laboratory:

- Bone marrow trephine ( $\geq 1$  cm) in a container of neutral buffered formalin (no other fixative allowed);
- Bone marrow aspirate
- Peripheral blood for MRD analysis.

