#### **7.1.3.4. Cytogenetics: FISH / TP53 Assays**

Cytogenetic profiles will use FISH probes to detect abnormalities in chromosomes 13q, 12, 11q, and 17p. TP53 mutational status will be measured. For subjects with unknown del 17p or del 11q or TP53 status, a peripheral blood or bone marrow sample (aspirate or biopsy) must be tested, in accordance with institutional policies and procedures within 180 days prior to randomization. For subjects without lymphocytosis at Screening, FISH and/or TP53 assessment should be performed on the bone marrow sample.

Existing FISH and TP53 results performed within the last 180 days prior to randomization, confirming the status of del 17p, del 11q and TP53 as per the assay specification will be

considered adequate for eligibility and stratification purposes, provided appropriate documentation is available.

For all subjects, screening peripheral blood (required) and marrow samples (where available) will be sent to the designated central laboratory to be tested for 17p-, 13q-, +12, and 11q-.

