#### **8.2.1.3. Cycles 7 - 33 Visits**

For subjects randomized to Treatment Arm A, **ibrutinib** therapy should be continued until disease progression, unacceptable treatment-related toxicity, or other reasons outlined in Section 9.2.

The following procedures will be performed on Day 1 ( $\pm 3$  days) of Cycles 7, 9, 11, 13, 15, 17, 19, 21, 23, 25, 27, 29, 31, and 33:

- PRO
- Adverse events
- Concomitant medications
- MRU
- Study drug compliance review (ibrutinib only)
- Physical exam
- Vital signs
- ECOG
- Hematology
- Serum chemistry (including creatinine clearance) (Cycles 7, 9, 11, and 13, then every 4 cycles)
- CT/MRI Scan (Cycles 9, 13, 17, 21, 25, 29, and 33)

- Bone marrow biopsy/aspirate (Cycle 9 only, unless appropriate for evaluation of PD or CR or to confirm MRD negativity in the peripheral blood)
- Overall response assessment (Cycles 9, 13, 17, 21, 25, 29, and 33)
- Biomarker assays (Cycles 9, 13, 17, 21, 25, 29, and 33)
- Flow cytometry blood assays (Cycles 9, 13, 17, 21, 25, 29, and 33)
- Cytogenetics: FISH panel (Cycle 9 Only)

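### Clonal evolution (Protocol 10.7.3.3) names trisomy 21 where the collection section and FISH panel have trisomy 12, and its any-time proportion gives the arm with more progressions more chances of detection

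*Protocol*

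**What the plan says.** Protocol 10.7.3.3 gives the only analysis definition in the two documents: "The proportion of subjects with new cytogenetic abnormalities (del 11q, del 17p, or trisomy 21". A catch-all for further abnormalities comes next. On methods and timing, the sentence ends: "detected by FISH, cytogenetics, or mutational analysis at any time post commencement of study treatment will be determined". It states no denominator and no rule for subjects with different numbers of samples.

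Protocol 7.1.3.3, under the heading on clonal evolution, describes "acquisition of new cytogenetic abnormalities defined as new del 11q, del 17p, or trisomy 12 by FISH, or other cytogenetic abnormalities". On timing it says: "A bone marrow sample should also be collected at the time of disease progression for examination of clonal evolution".

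Protocol 7.1.3.4 sets the assay: "Cytogenetic profiles will use FISH probes to detect abnormalities in chromosomes 13q, 12, 11q, and 17p". The central laboratory's screening panel covers the same four targets, including a gain of chromosome 12.

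After baseline, FISH is listed in Protocol 8.2.1.3 as "Cytogenetics: FISH panel (Cycle 9 Only", which footnote s of Appendix A confirms, and again among the suspected-progression procedures in 8.2.1.5. No other scheduled visit includes it.

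Protocol 10.7.3 says that exploratory endpoints are evaluated to compare the arms, using descriptive statistics. SAP Section 1 sends clonal evolution to a separate document.

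**The concern.** There are two issues, and they are independent of each other.

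First, the analysis definition names an abnormality that the specified FISH panel does not test and leaves out one that it does. Whoever writes the separate clonal-evolution plan would start from the wrong list.

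Second, the number of looks per subject depends on outcome. A subject who stays progression-free has one scheduled post-baseline FISH, at Cycle 9. A subject who progresses after Cycle 9 has two. If the any-time proportion is set side by side by arm, the arm with more progressions has more opportunities to record a new abnormality. A reader could take the resulting difference for a treatment effect on clonal evolution.

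**Working it through.** **1. Abnormality lists side by side**

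| Place | Named abnormalities |
|---|---|
| Protocol 7.1.3.3 | del 11q, del 17p, trisomy 12, other |
| Protocol 10.7.3.3 | del 11q, del 17p, trisomy 21, other |
| FISH probes, Protocol 7.1.3.4 | 13q, 12, 11q, 17p |

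Two of the three lists agree on chromosome 12. Chromosome 21 appears only in 10.7.3.3.

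**2. The plan's own event count**

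Inputs from Protocol 10.3: hazard ratio 0.55, two-sided 5%, 80% power, 1:1 allocation. Freedman's formula gives (1.960 + 0.842)² × (1.55/0.45)² = 7.849 × 11.864 = 93.1, rounded up to 94. This matches the plan. (Schoenfeld's formula gives 88.)

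**3. Expected PFS events by arm at 36 months**

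Further inputs from Protocol 10.3: medians 27 and 49.1 months, exponential PFS, 212 subjects at 18 per month.

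- Accrual period: 212/18 = 11.78 months.
- Hazards: Arm B ln 2/27 = 0.02567 per month; Arm A 0.55 × 0.02567 = 0.01412 per month.
- Probability of an event by 36 months, with uniform accrual: p = 1 − [exp(−24.22λ) − exp(−36λ)]/(11.78λ).
- Arm A: p = 0.346, or 36.6 of 106. Arm B: p = 0.537, or 56.9 of 106. Total 93.5, in line with the planned 94.

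Arm B therefore has 56.9/36.6 = 1.55 times as many events.

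**4. Effect on the any-time proportion when the arms do not differ**

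Assumptions, none of them given in the documents: every subject has a Cycle 9 sample; a share f of PFS events are progressions that yield a sample (60–100%); each sample has the same, independent detection chance q in both arms (5–20%).

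Samples per subject are 1 + f·p: 1.21–1.35 in Arm A and 1.32–1.54 in Arm B.

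Any-time proportion = 1 − (1 − q)(1 − f·p·q). The gap between arms is q(1 − q)·f·(0.537 − 0.346).

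| f | q | Arm A | Arm B | Gap (points, unrounded inputs) |
|---|---|---|---|---|
| 60% | 5% | 6.0% | 6.5% | 0.5 |
| 60% | 10% | 11.9% | 12.9% | 1.0 |
| 60% | 20% | 23.3% | 25.2% | 1.8 |
| 100% | 5% | 6.6% | 7.5% | 0.9 |
| 100% | 10% | 13.1% | 14.8% | 1.7 |
| 100% | 20% | 25.5% | 28.6% | 3.1 |

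Of 106 subjects, 0.5 to 3.1 points is 0.6 to 3.2 subjects.

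**The case against.** The strongest reply is that little turns on either issue.

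- Both sections add a catch-all for other cytogenetic abnormalities, so a new trisomy 12 would still be counted. Section 10.7.3.3 also admits conventional cytogenetics and mutational analysis, so trisomy 21 is beyond the FISH panel but not beyond every listed method. Both points stand. They limit the damage but do not make the list correct.
- The SAP defers this analysis, and the separate document may already set denominators. That stands too: the documents show that 10.7.3.3 gives no denominator, not that the final analysis will lack one.
- The endpoint is exploratory and descriptive, so no test depends on it. That is correct. Protocol 10.7.3 nevertheless intends a comparison between arms.

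Three stronger readings are tempting, and the documents do not support them.

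- A reader might infer that 7.1.3.3 and 10.7.3.3 contradict each other on timing, progression in one and any time in the other. Section 7.1.3.3 asks for a marrow sample at progression in addition to others and puts no time limit on the definition.
- A reader might count progression samples only and, at 20% detection, get 0.20 × 53.7% = 10.7% against 0.20 × 34.6% = 6.9%, a gap of about 3.8 points. That leaves out the Cycle 9 FISH scheduled in both arms and treats every PFS event as a sampled progression.
- A reader might infer that everyone without a PFS event lacks a progression sample. FISH is triggered by suspected progression, so some subjects never confirmed as progressing will also be tested.

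**Conclusion.** The trisomy 21 entry is an error in the analysis definition. It conflicts with 7.1.3.3 and with the panel in 7.1.3.4, and the catch-all only partly repairs it.

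The unequal-sampling point also holds, as an expectation and not a certainty. It comes from progression-triggered testing and would arise with either abnormality list. Under the protocol's PFS assumptions the spurious excess in Arm B is about 0.5 to 3 points.

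That range rests on the assumed detection rates, the assumed share of events sampled, and a Cycle 9 sample for everyone. Subjects who progress before Cycle 9 would have one sample instead of two, which narrows the gap. A higher detection chance at progression than at Cycle 9 would widen it.

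This is a minor point. The primary analysis, alpha and power do not change.

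**What to change.** In Protocol 10.7.3.3, change trisomy 21 to trisomy 12, so that the list matches 7.1.3.3 and the FISH panel.

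In 10.7.3.3 and in the separate clonal-evolution document that the SAP refers to, replace the single any-time proportion with two:

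- **Cycle 9**: new abnormalities among subjects with baseline and Cycle 9 FISH. This is the comparison between arms, because each subject has one look at a fixed time.
- **Progression**: new abnormalities among subjects with baseline and progression FISH, reported separately, with a note that this is a post-randomisation subset and not a randomised comparison.

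Give the number sampled by arm for both, since Cycle 9 samples will also be missing for subjects who progressed or left earlier.

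The cost is wording in two documents, slightly smaller denominators and one extra table. No samples or visits are added.

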#### **10.7.3.4. Predictive Biomarkers of Efficacy and/or Mechanism of Resistance**

Biomarker exploratory analyses are planned to identify biomarkers that may associate with response (or resistance) to ibrutinib. These biomarkers include but are not limited to secreted protein analysis, genomic and expression analysis.

#### **10.7.3.5. Medical Resource Utilisation**

Parameters collected for MRU associated with the therapy include number of hospitalizations, number of emergency department visits, number of blood product transfusions, and number of use of hematopoietic growth factors.

#### **10.7.3.6. Sparse Pharmacokinetic Characteristics of Ibrutinib**

The plasma concentration data for ibrutinib will be summarized using descriptive statistics at each timepoint. Population PK analysis of plasma concentration-time data of ibrutinib will be performed using nonlinear mixed-effects modeling. Data may be combined with data from other studies to support a relevant population PK model. Available subject characteristics (eg, demographics, laboratory variables, genotypes, etc.) will be tested as potential covariates affecting PK parameters. Details will be given in a population PK analysis plan and the results of the population PK analysis will be presented in a separate report.

**10.7.3.7. Genetic and Molecular Prognostic Markers**

Genetic and molecular prognostic markers will be summarized with descriptive statistics.

**10.8. Safety Analyses**

Safety summaries will include tabulations in the form of tables and listings. The safety analysis will be conducted using the safety population. Subjects will be analyzed according to the actual treatment received.

Study drug exposure including duration and dosage as well as dose modifications of study drug including dose reduction, dose delay, missed doses, and dose interruption will be summarized.

**10.8.1. Adverse Events (AEs)**

Adverse events (AEs) will be graded by the Investigator according to the NCI CTCAE v4.03 for non-hematological AEs. Hematologic toxicity will be assessed by the IWCLL 2008 criteria for grading hematologic toxicity in CLL studies. Verbatim descriptions of AEs will be coded using the current version of the Medical Dictionary for Regulatory Activities (MedDRA). Adverse events that started from the date of the first dose of the first study drug up to 30 days after the date of the last dose of the last study drug, or the first date starting new anticancer therapy, whichever is earliest, are considered treatment-emergent except treatment related AEs. Any treatment related AE will be considered treatment-emergent regardless of the start date of the event. Any event that is present at baseline but worsens in severity or is subsequently considered treatment-related by the investigator will also be considered as treatment-emergent. All-treatment emergent AEs will be summarized by treatment arm. The incidence rates of treatment-emergent AEs will be summarized by System Organ Class (SOC), preferred term, toxicity grade, and relationship to study drug. In addition, SAEs, Grade 3 or above AEs, AEs leading to study treatment discontinuation, delay, reduction, or interruption, AEs leading to death, and events of special interest will be summarized. Multiple occurrence of the same event in a given subject will be counted once at the maximum severity and strongest relationship to study drug.

AEs leading to death and non-fatal SAEs will be listed by subject and tabulated by preferred term.

**10.8.2. Laboratory Evaluations**

All laboratory values will be converted to standard international (SI) units and classified as normal, low, or high based on normal ranges supplied by the central laboratory. Hematologic parameters including platelet count, hemoglobin, and neutrophils will be assessed by the IWCLL 2008 criteria for grading hematologic toxicity in CLL studies. All other gradable laboratory parameters will be graded using the NCI CTCAE v4.03.

Subjects with values outside the normal range will be flagged and summarized by treatment arm. Selected gradable laboratory parameters will be summarized by treatment arm using shift tables. A separate listing and table will be provided to identify and summarize subjects with markedly abnormal changes. In addition, changes from baseline in quantitative parameters will be summarized descriptively by treatment arm at scheduled timepoints.

### **10.8.3. Vital Signs**

Vital signs will be classified as normal, low, or high; and change from baseline will be summarized descriptively by treatment arm at scheduled timepoints. Subjects with markedly abnormal changes will be listed and tabulated.

### **10.8.4. Obinutuzumab-related Infusion Reactions**

The proportion of subjects experiencing i) no infusion reactions, ii) Grade 1 and/or Grade 2 infusion reactions or iii) Grade 3 and/or Grade 4 infusion reactions will be evaluated for each treatment arm for i) Cycle 1 of obinutuzumab and ii) all other cycles of obinutuzumab (Cycles 2 and subsequent cycles).

The secreted protein analysis will also be used to evaluate the impact of ibrutinib on obinutuzumab-related infusion reactions. Plasma will be collected pre-dose ibrutinib/chlorambucil, immediately prior to infusion of obinutuzumab, and 2 and 4 hours into the obinutuzumab infusion on Day 1. The samples will be evaluated for secreted proteins related to infusion reactions, such as IL-6, TNF-alpha, as well as other cytokines and chemokines.

### **10.8.5. Other Safety Assessments**

Physical examination, ECG, and eye examination results will be listed.

## **11. ADVERSE EVENT REPORTING**

Timely, accurate, and complete reporting and analysis of safety information from clinical studies are crucial for the protection of subjects, investigators, and the Sponsor, and are mandated by regulatory agencies worldwide. The Sponsor has established Standard Operating Procedures in conformity with regulatory requirements worldwide to ensure appropriate reporting of safety information; all clinical studies conducted by the Sponsor or its affiliates will be conducted in accordance with those procedures.

### **11.1. Definitions**

#### **11.1.1. Adverse Events**

An AE is any untoward medical occurrence in a subject administered a pharmaceutical product and which does not necessarily have a causal relationship with this treatment. An AE can therefore be any unfavorable and unintended sign (including a clinically significant abnormal

laboratory finding, for example), symptom, or disease temporally associated with the use of an investigational study drug, whether or not considered related to the study drug (ICH-E2A 1995).

For the purposes of this clinical study, AEs include events which are either new or represent detectable exacerbations of pre-existing conditions.

The term “disease progression” should not be reported as an adverse event term. As an example, “worsening of underlying disease” or the clinical diagnosis that is associated with disease progression should be reported.

Adverse events may include, but are not limited to:

- Subjective or objective symptoms provided by the subject and/or observed by the Investigator or study staff including laboratory abnormalities of clinical significance.
- Any AEs experienced by the subject through the completion of final study procedures.
- AEs not previously observed in the subject that emerge during the protocol-specified AE reporting period, including signs or symptoms associated with the underlying disease that were not present before the AE reporting period
- Complications that occur as a result of protocol-mandated interventions (eg, invasive procedures such as biopsies).

The following are NOT considered AEs:

- **Pre-existing condition:** A pre-existing condition (documented on the medical history CRF) is not considered an AE unless the severity, frequency, or character of the event worsens during the study period.
- **Pre-planned or elective hospitalization:** A hospitalization planned before signing the informed consent form is not considered an SAE, but rather a therapeutic intervention. However, if during the pre-planned hospitalization an event occurs, which prolongs the hospitalization or meets any other SAE criteria, the event will be considered an SAE. Surgeries or interventions that were under consideration, but not performed before enrollment in the study, will not be considered serious if they are performed after enrollment in the study for a condition that has not changed from its baseline level. Elective hospitalizations for social reasons, solely for the administration of chemotherapy, or due to long travel distances are also not SAEs.
- **Diagnostic Testing and Procedures:** Testing and procedures should not to be reported as AEs or SAEs, but rather the cause for the test or procedure should be reported.
- **Asymptomatic Treatment Related Lymphocytosis:** This event should also not be considered an AE. Subjects with treatment-related lymphocytosis should remain on study treatment and continue with all study-related procedures.

### 11.1.2. Serious Adverse Events

A serious adverse event based on ICH and EU Guidelines on Pharmacovigilance for Medicinal Products for Human Use is any untoward medical occurrence that at any dose:

- Results in death (ie, the AE actually causes or leads to death).
- Is life-threatening. Life-threatening is defined as an AE in which the subject was at risk of death at the time of the event. It does not refer to an event which hypothetically might have caused death if it were more severe. If either the Investigator or the Sponsor believes that an AE meets the definition of life-threatening, it will be considered life-threatening.
- Requires inpatient hospitalization >24 hours or prolongation of existing hospitalization.
- Results in persistent or significant disability/incapacity (ie, the AE results in substantial disruption of the subject's ability to conduct normal life functions).
- Is a congenital anomaly/birth defect.
- Is an important medical event that may not result in death, be immediately life-threatening or require hospitalization, but may be considered an SAE when, based upon appropriate medical judgment, the event may jeopardize the subject or subject may require intervention to prevent one of the other outcomes listed in this definition. Examples of such events are intensive treatment in an emergency department or at home for allergic bronchospasm, blood dyscrasias, or convulsion that does not result in hospitalization; or development of drug dependency or drug abuse.

Given that the Investigator's perspective may be informed by having actually observed the event, and the Sponsor is likely to have broader knowledge of the drug and its effects to inform its evaluation of the significance of the event, if either the Sponsor or the Investigator believes that the event is serious, the event will be considered serious.

